12. STATISTICAL ANALYSIS

- *Describe how your data will be used to test the hypotheses.*
- *State clearly what variables will be tested and what statistical tests will be used.*
- *Include sample size calculations.*
- *If this is a pilot study, state which variables will be examined for hypothesis generation in later studies.*

For our primary outcome measure, we will investigate whether tVNS paired in a closed loop with robotic therapy changes peak amplitude EMG activation in muscle groups along the shoulder and elbow. We hypothesize that upper extremity flexor synergy will be significantly improved when active tVNS is applied during extensor movements as compared to a sham condition, and will lead to an increase in EMG peak activation at the triceps brachii (elbow extensor muscle). This will be examined with a 2x3 ANOVA with condition (active stimulation vs. sham) and time (peak amplitude of EMG activation during extensor movements at admission, discharge, and follow-up) as factors.

For our secondary outcome measure, we will test whether active tVNS during extensor movements paired in a closed loop with intensive robotic intervention (9 sessions) significantly improves upper extremity motor function as compared to sham tVNS paired with intensity-matched robotics. This will be examined with a 2x3 Friedman ANOVA with condition (active vs. sham tVNS) and time (upper extremity fugl meyer score at admission, discharge, and 3 month FU) as factors.

Since this is a pilot study, there are presently no data from which we can derive a power calculation. However, we propose to enroll 36 subjects, in order to achieve a target of at least fifteen subjects per treatment group and also allow for a 10-15% drop out rate. In our extensive past experience with upper limb hemiparesis rehabilitation studies, 10-15 subjects per treatment group is required at minimum to capture a measurable treatment response. Additionally, two other early pilot studies investigating post-stroke upper limb motor rehabilitation combined with VNS found a significant improvement in motor performance with nine and fourteen subjects per treatment group (e.g. sham and active VNS), respectively [8 & 41].

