4. OBJECTIVE(S)/SPECIFIC AIMS AND HYPOTHESES

- *A concise statement of the goal(s) of the current study.*
- *The rationale for and specific objectives of the study.*
- *The goals and the hypothesis to be tested should be stated.*

Specific Aim 1: To evaluate whether 3 weeks of robotic therapy paired with tVNS delivered only during extensor movements will significantly change

EMG activation patterns of up the upper extremity during unassisted gravity-eliminated movements in approximately 18 patients with chronic post-stroke hemiparesis compared to sham condition.

In patients with chronic upper-limb hemiparesis post-stroke, we will use a within-subjects repeated measure design to determine if 9 sessions of active tVNS during only extensor movements significantly alters EMG activation of the biceps brachii and triceps as compared to a sham condition.

Specific Aim 2: To determine whether 3 weeks of robotic therapy paired with tVNS will significantly improve clinical measures of upper extremity motor function in approximately 18 patients with chronic hemiparesis after stroke compared to a sham condition.

We will use a within-subjects repeated measures design to determine if 9 sessions of robotic therapy paired with active tVNS during only extensor movements significantly improves upper extremity motor function in patients with chronic post-stroke hemiparesis as compared to sham tVNS paired with robotic therapy.

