10. ENDPOINTS

- *Describe the primary and secondary study endpoints*
- *Describe any primary or secondary safety endpoints*

The primary measure of treatment efficacy will be an increase in EMG activation peak amplitude for upper extremity extensor muscles of at least 10%. The secondary measure of treatment efficacy will be an improvement in Upper Extremity Fugl Meyer score of at least 3 points (out of 66).

The primary safety endpoint will be any serious adverse events of suspected relationship with the tVNS investigational device. Any serious adverse events will be reported to the PI, research team, and IRB immediately for determination if the study should be discontinued. However, given that there were no serious adverse device effects of implanted VNS in individuals with stroke [8], it is anticipated that transcutaneous auricular vagus nerve stimulation will pose an even lower risk.

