11. RESEARCH PROCEDURES

- *Include a detailed description of all procedures to be performed on the research subject and the schedule for each procedure.*
- *Include any screening procedures for eligibility and/or baseline diagnostic tests*
- *Include procedures being performed to monitor subjects for safety or minimize risks*
- *Include information about drug washout periods*
- *If drugs or biologics are being administered provide information on dosing and route of administration*
- *Clearly indicate which procedures are only being conducted for research purposes.*
- *If any specimens will be used for this research, explain whether they are being collected specifically for research purposes.*
- *Describe any source records that will be used to collect data about subjects*
- *Indicate the data to be collected, including long term follow-up*

Consecutive Sessions of tVNS during robotic therapy intervention

Thirty-six patients with chronic, post-stroke upper extremity hemiparesis will be accepted into this study, and randomized to receive either sham or active tVNS treatment coupled with robotic therapy. There will be 2-3 baseline measurement periods prior to treatment. Following the lead-in period, subjects will participate in a training period consisting of approximately 1 hour sessions robotic therapy paired with tVNS 3x/week for 3 weeks, for a total of 9 sessions. Following the training period, subjects will complete clinical and objective measures both immediately at discharge and again a 3-month follow-up visit.

Lead-in Period

- Week 1, Visit 1 (approximately 90 minutes)
 - Baseline clinical outcome measures
 - Instrumental measures with EMG
 - Medical screening
 - Consent
- Week 1, Visits 2-3 (approximately 60 minutes each)
 - Baseline clinical outcome measures
 - Instrumental measures with EMG

Training Period

- Weeks 2-4, Visits 4-12 (approximately 60 minutes)
 - robotic therapy + tVNS

- Device tolerance questionnaires (every session)

Discharge Evaluation

- Week 4, Visit 13 (approximately 60 minutes)
 - Clinical outcome measures
 - Instrumental measures with EMG

Follow-Up Evaluation

- Week 16, Visit 14 (approximately 60 minutes)
 - Clinical outcome measures
 - Instrumental measures with EMG

**Phase II
Schedule**

	Screen 1	Screen 2	Screen 3	taVNS Tx + robotics	DC eval	3 mo FU
	Visit 1	Visit 2	Visit 3	Visit 4-12	Visit 13	Visit 14
Informed Consent	X					
Medical Hx	X					
Demographic Info	X					
Inclusion Criteria	X					

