Electrical activity of the muscle will be differentially recorded during tVNS sessions using a bipolar electrode montage placed on the belly of the muscle. Recordings will be made from the biceps and triceps brachii, pectoralis major, rhomboideus, and/or the deltoids, which are some of the important muscles responsible for flexion and extension of the shoulder and elbow.

Randomization

Subjects will be stratified by established clinical impairment levels based upon admission Upper Extremity Fugl Meyer scores (low function <23 & moderate function 23-44) such that there are an equal number of low and high functioning patients in each treatment group. Subjects will then be randomized to either the active or sham tVNS group [28]. Assignment will be predetermined by a randomized assignment list, created prior to the enrollment of the first subject by an investigator from the CBEM team who is not directly involved in subject treatment. There will be concealed allocation of treatment assignment such that investigators involved in subject screening, consent, and clinical scoring will be blinded to treatment condition.

Blinding

This will be a double-blind pilot study in which subjects will be randomly assigned to either the sham or active tVNS conditions. Subjects will be told that they have a 50-50 chance of receiving either active or sham stimulation, but they will not be told which condition they receive. Additionally, the assigned clinical evaluators will remain blinded to condition. For each study session, stimulation condition will be programmed into the device by the RA or members of the CBEM team who are not performing clinical measures.

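### The primary EMG analysis never says which of the 2-3 baseline recordings is the admission value, nor which ANOVA term and visit decide; the mean of the scheduled baselines should be fixed in advance and used

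*Combined protocol and SAP*

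**What the plan says.** Section 12 (Statistical Analysis) gives the whole primary analysis in one sentence: "This will be examined with a 2x3 ANOVA with condition (active stimulation vs. sham) and time". The levels of time are "peak amplitude of EMG activation during extensor movements at admission, discharge, and follow-up". The hypothesis just before it is a rise in triceps peak activation under active stimulation relative to sham. No term of the ANOVA is named as deciding, and neither post-treatment visit is named as primary.

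Section 10 (Endpoints) does not settle it. It reads "The primary measure of treatment efficacy will be an increase in EMG activation peak amplitude for upper extremity extensor muscles of at least 10" per cent, with no visit and no reference baseline.

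Section 11 (Research Procedures) states: "There will be 2-3 baseline measurement periods prior to treatment". The lead-in list puts "Instrumental measures with EMG" at Visit 1 and again at Visits 2-3, and the schedule table marks the instrumental assessment at all three screening visits, at discharge (Visit 13) and at 3 months (Visit 14). It is not marked at the treatment visits (4-12). The Electromyography paragraph of the same section says instead: "Electrical activity of the muscle will be differentially recorded during tVNS sessions". Aim 1 in Section 4 refers to "EMG activation patterns of up the upper extremity during unassisted gravity-eliminated movements in approximately 18 patients".

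**The concern.** The pre-treatment EMG value is one of the three outcome levels, so how it is formed enters the primary test directly. The word admission could mean Visit 1, the last lead-in visit, or a mean. With about 15 patients per arm, these can give different p-values, and the plan leaves the choice until after the data are seen. Using one baseline also leaves one or two scheduled recordings unused in the primary test.

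A significant interaction on 2 degrees of freedom shows that the arms changed differently over time. It does not say whether the claim concerns discharge, 3 months or both, so the comparisons that follow it need to be fixed too.

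**Working it through.** **Inputs from the protocol.** Enrolment is 36, with at least 15 per group after 10-15% dropout (Section 12). This reproduces: 30/(1 - 0.15) = 35.3, rounded up to 36; 30/(1 - 0.10) = 33.3, rounded up to 34. There are two or three EMG baselines and two post-treatment visits (Section 11).

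**Inputs assumed.** The protocol gives no SD, correlation, effect size or alpha. I take two-sided 5%, complete data on 15 per arm, unit variance at each visit, and an effect of 0.8 SD at discharge and 3 months. The correlation between any two visits is 0.7, with 0.5 and 0.8 as the range. Because all baselines fall in Week 1, I also take baselines correlated 0.9 with each other and 0.7 with later visits.

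**Why averaging helps.** With a common correlation r, the per-patient variance of the change from the mean of k baselines is (1 - r)(1 + 1/k). At r = 0.7:
- one baseline: 0.3 x 2 = 0.60
- two: 0.3 x 1.5 = 0.45
- three: 0.3 x 1.333 = 0.40

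If the three baselines correlate 0.9 with each other, their mean has variance 0.9 + 0.1/3 = 0.933, and the change has 1 + 0.933 - 1.4 = 0.533. The gain is then much smaller.

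**Interaction power, one baseline.** The arm differences are (0, 0.8, 0.8), with sum of squares about their mean 0.64 x 2/3 = 0.427. The noncentrality is (15/2) x 0.427/(1 - 0.7) = 10.67. With 2 and 56 degrees of freedom, power is 82%.

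**Interaction power by number of baselines** (simulation, at least 20,000 trials per scenario, sustained effect):

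| Correlation | One baseline | Mean of two | Mean of three |
|---|---|---|---|
| 0.7 throughout | 82% | 91-92% | 94% |
| 0.7, baselines 0.9 | 82% | 85% | 86% |
| 0.5 throughout | 59% | 70% | 74-75% |
| 0.8 throughout | 95% | 99% | 99% |

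Under no effect, at 0.7, the interaction rejects in 5.1% of trials with one baseline and 5.3% with the mean of three, so the test is sound either way. For an effect at discharge only, at 0.7, averaging three baselines lifts it from 82% to 89%.

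**Cost of the open choice.** Under no effect, if significance with the first, the last or the mean baseline may each count, the rejection rate is about 9% at a common correlation of 0.7 and about 7.5% when baselines correlate 0.9.

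**The alternative of one named contrast** (analysis of covariance, three-baseline mean in every column, correlation 0.7):

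| True effect (SD) | Interaction | Average of discharge and 3 months | Discharge |
|---|---|---|---|
| 0.8 at both visits | 94% | 99% | 91% |
| 0.8 then 0.4 | 83% | 89% | 91% |
| 0.4 then 0.8 | 83% | 89% | 38% |
| 0.8 at discharge only | 89% | 57% | 91% |
| 0.8 at 3 months only | 89% | 57% | 5% |

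Neither contrast is ahead of the interaction in every row.

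**The case against.** The strongest reply is that the plan is a pilot, its hypothesis is a rise relative to sham, and any statistician would take the interaction as the test. That stands as to the term. A reader might infer a larger error: if either the condition main effect or the interaction could count, the type I error would be about 10%. The documents do not support that reading, because the main effect averages in the pre-treatment level and does not answer the stated hypothesis. What the reply does not reach is the baseline and the visit, which no section defines.

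A reader might also infer that the ANOVA is wrong, or that a baseline-adjusted model with one contrast would plainly be better. Neither follows. The interaction keeps its 5% level, and the second table shows a trade-off that depends on a time course the protocol does not predict. Aim 1 speaks of the effect of three weeks of therapy ("To evaluate whether 3 weeks of robotic therapy paired with tVNS delivered only during extensor movements will significantly change"), which leans towards discharge but does not name it as the deciding visit.

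It is tempting to add that, at 0.7, the verdict differs between Visit 1 and the three-baseline mean in about 14.5% of trials with a sustained effect. Almost all of this (about 13.3 points) is trials that become significant with the mean. It is the power gain counted again, not a separate harm.

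Finally, a reader might infer from the Electromyography paragraph that the outcome recording itself is undefined. Section 12 fixes the outcome times at admission, discharge and follow-up, the schedule has matching EMG visits, and recording during sessions can be additional. A clarifying sentence is enough.

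**Conclusion.** The gap is real and of moderate size. The admission value is undefined although two or three EMG baselines are scheduled. The deciding term is inferable but unstated, and the deciding visit is unnamed. The planned interaction is a valid test. Leaving the baseline open allows about 7 to 9% type I error in place of 5%, if the choice is made on the data. Using one baseline forgoes power: at an assumed correlation of 0.7 and a sustained 0.8 SD effect, 82% against 91-92% with two and 94% with three, or 86% with three if the Week 1 baselines correlate 0.9.

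Every power figure rests on assumed values, since the protocol supplies none. The direction does not: averaging the baselines raised power in every scenario run. This should be corrected before unblinding. It does not call the sample size or the design into question.

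**What to change.** Add one paragraph to Section 12:
- Define baseline (admission) triceps peak EMG as the mean of the available Visit 1-3 values, and use it in the primary analysis. The reference for the percentage threshold in Section 10 should be the same value, with its visit named.
- State that the condition-by-time interaction decides at two-sided 5%.
- Fix the active-versus-sham comparisons at discharge and at 3 months that will interpret it.

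In Section 11, say that EMG recorded in treatment sessions is additional to the outcome recordings at Visits 1-3, 13 and 14, or reconcile that paragraph with the schedule and with Aim 1.

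The cost is wording only. The schedule already contains the recordings, so no visit or measurement is added. If the team has a firm view of the time course, it may instead name one baseline-adjusted contrast (discharge, or the average of discharge and 3 months). The price is the loss shown above when the effect appears elsewhere: 57% against 89% for the averaged contrast with a one-visit effect, and about 5% for the discharge contrast with an effect at 3 months only.

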16. WITHDRAWAL OF SUBJECTS

- *Describe anticipated circumstances under which subjects will be withdrawn from the research without their consent*
- *Describe procedures for orderly termination*
- *Describe procedures that will be followed when subjects withdraw from the research, including partial withdrawal from procedures with continued data collection.*

Study participation is voluntary, and a subject can withdraw at any time by notifying a member of the research team. It is also possible that a subject may be withdrawn from a study without his or her consent. Reasons for such withdrawal may include failure to keep study appointments, changes in medications or medical history such that the subject no longer meets inclusion criteria, experiencing an adverse event that is related or potentially related to the study intervention, or study cessation. Once a subject is withdrawn from the study, no new data will be collected, but previously collected data will be kept and may be used.

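### The primary 2x3 repeated-measures ANOVA needs all three visits, so a patient who misses week 16 also drops out of the discharge comparison, and no stated rule prevents it

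*Combined protocol and SAP*

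**What the plan says.** - **Primary test (Section 12).** "This will be examined with a 2x3 ANOVA with condition (active stimulation vs. sham) and time" as factors. The time levels are given as "peak amplitude of EMG activation during extensor movements at admission, discharge, and follow-up".
- **Design (Section 4, Aim 1).** "we will use a within-subjects repeated measure design to determine if 9 sessions of active tVNS during only extensor movements" alters EMG activation compared with sham. Section 11 randomises patients to active or sham, so condition is a between-patient factor and time is the repeated one.
- **Visits (Section 11).** Discharge evaluation is visit 13 in week 4. Follow-up is visit 14 in week 16.
- **Secondary test (Section 12).** For Fugl-Meyer over the same three times: "This will be examined with a 2x3 Friedman ANOVA with condition (active vs. sham tVNS) and time".
- **Sample size (Section 12).** Thirty-six patients are to be enrolled to "achieve a target of at least fifteen subjects per treatment group and also allow for a 10-15% drop out rate". There is no power calculation.
- **Withdrawal (Section 16).** Nothing new is collected after withdrawal, but "previously collected data will be kept and may be used".

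The document defines no analysis population and contains no intention-to-treat statement, imputation rule or mixed model.

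**The concern.** A conventional repeated-measures ANOVA works on complete rows: each patient needs a value at every level of the time factor. One missing week-16 EMG removes the whole row, including the admission and discharge values already recorded. The discharge contrast is the comparison closest to treatment, and it would be thinned by events up to 12 weeks later.

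Two things are at stake. Precision is lost in a trial that aims for only about 15 patients per arm. The comparison also moves from all randomised patients with a discharge value to those who later returned. If the reasons for not returning relate to outcome and differ by arm, randomisation no longer protects it. Enrolling extra patients restores the headcount but does not change who is analysed. Section 16 permits use of earlier data but names no method, so the decision could be taken after the data are seen.

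**Working it through.** **1. The plan's own figure.** Target 15 per arm, 30 in total. At 15% drop-out, 30 / (1 - 0.15) = 35.3, or 36 when rounded up. At 10%, 30 / (1 - 0.10) = 33.3, or 34. The stated 36 is reproduced at the upper rate. Patients are told the odds are 50-50, so I assume 18 per arm.

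**2. Does the named method drop incomplete patients?** A standard repeated-measures ANOVA routine was given 36 patients with 5 third visits missing, testing the within-patient time factor. It refused the data as unbalanced. Those patients must be removed before it will run.

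**3. How many patients?** Complete rows: 36 x 0.90 = 32.4 and 36 x 0.85 = 30.6. Losses: 3.6 and 5.4, so about 4-5. This is an upper bound for discarded discharge values. It applies only if all drop-out falls between weeks 4 and 16, and the document does not give the timing. Patients lost before discharge have no discharge value under any method.

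**4. Precision.** The standard-error ratio for the discharge contrast is sqrt(36 / n).
- 10% loss: sqrt(36 / 32.4) = 1.054.
- 15% loss: sqrt(36 / 30.6) = 1.085.
- Exactly 15 per arm left: sqrt(36 / 30) = 1.095.

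A simulation of change from admission to discharge (8,000 trials per scenario) assumed a visit correlation of 0.7. The SD of change is then sqrt(2 x 0.3) = 0.775 in units of the outcome SD. Random 15% loss raised the standard error from 0.257 to 0.280, a ratio of 1.089.

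**5. Bias.** Same simulation, assumed true discharge effect 0.50 SD:

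| Loss after discharge | All discharge data, 10% / 15% | Completers only, 10% / 15% |
|---|---|---|
| Random in both arms | 0.50 / 0.50 | 0.50 / 0.50 |
| Poor responders, same rule within each arm | 0.50 / 0.50 | 0.50 / 0.50 |
| Poor responders in active, random in sham | 0.50 / 0.51 | 0.59 / 0.66 |

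Poor responders were the lowest third of an arm by discharge change, each lost with probability three times the overall rate. The shift in the last row is 0.592 - 0.499 = 0.09 at 10% and 0.655 - 0.505 = 0.15 at 15%. Because selection is by rank within the arm, it does not depend on the true effect.

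A separate simulation assumed no true effect, correlations of 0.6, 0.6 and 0.48, and losses of about 3.4 of 18 active and 1.8 of 18 sham. Completers-only showed a false discharge benefit of 0.15 SD (baseline-adjusted) or 0.18 SD (change score), against 0.00 using all discharge data. Weaker or stronger dependence on outcome gave 0.09-0.25.

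**The case against.** **The exclusion is inferred.** Section 12 says only ANOVA with two factors and never mentions completers. That is correct. An ordinary two-way ANOVA would keep the incomplete patients, but it would treat three visits of one patient as independent and would contradict Section 4. Neither reading is satisfactory.

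**Drop-out inflation shows nothing about the analysis set.** This stands. A reader might infer from the 36-to-30 arithmetic that the sponsor intends a completers' analysis. The document does not support that, because the same inflation is routine in trials analysed by intention to treat.

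**The bias is built into the scenario.** This largely stands. It needs outcome-related loss that differs by arm, and two of the three loss patterns above gave none. The mixed model recovers the truth here because loss was made to depend only on observed values. The route to unequal loss is also weak. Stimulation is confined to visits 4-12, so device-related withdrawals would mostly come before discharge, where neither method has a discharge value.

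**Sphericity.** A reader might add that unequally spaced visits inflate the false-positive rate. The document gives no correlations. Under the 0.6, 0.6, 0.48 assumed above, epsilon is 0.968 and simulated error was 4.8%, so no inflation is shown. A standard correction would deal with it in any case.

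**It is a pilot.** True, but Section 12 frames a test of active against sham, and few patients make each usable record matter more.

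**Conclusion.** The point holds as a consequence of the named method, not as a stated intention. The primary ANOVA, read with the repeated-measures design, discards discharge EMG from any patient without a week-16 value, and nothing in the document overrides this.

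The certain cost is modest: at most about 4-5 of 36 patients and up to about 9% on the standard error of the discharge contrast, less if some drop-out comes before discharge. Bias is conditional. It is nil under random loss or under the same outcome-related loss in both arms, and roughly 0.1-0.2 SD in favour of active if poor responders leave only from that arm. The bias figures rest on assumed correlations and loss mechanisms, since the document supplies neither. The change should be made because it is cheap, not because a false result is likely.

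**What to change.** In Section 12, make the primary analysis a likelihood-based mixed model for repeated measures:

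- Outcomes: EMG at admission, discharge and follow-up, or admission EMG as a baseline covariate with the two later visits as outcomes. State which.
- Terms: arm, categorical visit and arm-by-visit, with unstructured covariance and a small-sample degrees-of-freedom correction such as Kenward-Roger.
- Analysis set: all randomised patients with any post-baseline EMG, in their assigned arm.
- Estimates: the discharge and 3-month contrasts, both taken from this model, with the missing-data assumption stated.
- Sensitivity: the completers' ANOVA.

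In Section 16, change 'may' to 'will' for the use of data collected before withdrawal. The Friedman analysis of Fugl-Meyer also needs complete blocks, so give it an analysis set and missing-data rule at the same time.

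The cost is wording in two sections and a standard software procedure. No extra patients or visits are needed.

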2. BRIEF SUMMARY OF RESEARCH

- *The summary should be written in language intelligible to a moderately educated, non-scientific layperson.*
- *It should contain a clear statement of the rationale and hypothesis of your study, a concise description of the methodology, with an emphasis on what will happen to the subjects, and a discussion of the results.*
- *This section should be ½ page*

Stroke is the fifth leading cause of death and the leading cause of serious long-term disability in the U.S. [1]. Post-stroke impairment is often characterized by hemiparesis or weakness of the upper and lower limbs, rendering the individual dependent for most activities of daily living. Traditional stroke rehabilitation medicine consists of a combination of one-on-one treatment and group therapy with physical, occupational and speech therapists, focusing on both labor-intensive motor training of the affected limbs, as well as compensatory training of the unaffected side of the body. Even with aggressive standard rehabilitation, 65 percent of patients cannot incorporate their affected hand in functional activities six months after stroke, and only 25 percent of patients return to the level of life participation equivalent to that of community-matched healthy controls [2].

We have previously demonstrated that robotic therapy provides functionally and clinically significant benefits to upper limb motor recovery after stroke, and has been consequently acknowledged by the American Heart Association as an effective form of stroke rehabilitation [3-5]. Robotic intervention operates through a series of interactive motors with low impedance which move a patient's limb when the patient cannot move and progressively intervene less as the patient improves. The advantage of this technology is to deliver reproducible movement without tiring, increasing the level of training intensity and potentially decreasing the level of impairment. Though the clinical benefit of robotic interventions to reduce motor impairment after stroke is well established, the results are generally not curative.

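### The Friedman test named for the Fugl-Meyer score has no between-patient factor, so it cannot compare active with sham tVNS

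*Combined protocol and SAP*

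**What the plan says.** Section 12 states the Fugl-Meyer question as a comparison of arms: whether active tVNS with robotic therapy "significantly improves upper extremity motor function as compared to sham tVNS paired with intensity-matched robotics". The next sentence gives the test: "This will be examined with a 2x3 Friedman ANOVA with condition (active vs. sham tVNS) and time". The three time levels are admission, discharge and the 3-month visit.

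The preceding paragraph uses a similar layout for the primary EMG outcome: "This will be examined with a 2x3 ANOVA with condition (active stimulation vs. sham) and time".

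The design is parallel-group. Section 11 has patients "randomized to receive either sham or active tVNS treatment coupled with robotic therapy", and under Randomization, after stratifying by admission Fugl-Meyer (below 23 against 23 to 44), "Subjects will then be randomized to either the active or sham tVNS group". The visit schedule has one treatment block and no crossover or washout.

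Section 10 makes a Fugl-Meyer gain of at least 3 points the secondary efficacy measure but attaches no test to it. Section 11 labels Fugl-Meyer as primary among the clinical measures. No section other than Section 12 names a test for it.

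**The concern.** The sentence asks a within-patient rank test to carry a between-patient factor. An ordinary two-way ANOVA with repeated measures can hold condition and time together, but Friedman's test cannot.

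The analyst would then have three ways forward:

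- **Pool all patients and run Friedman over the three visits.** This tests change over time. Both arms receive robotic therapy, and Section 2 says "robotic therapy provides functionally and clinically significant benefits to upper limb motor recovery after stroke", so some change in both arms is expected. A significant result would say nothing about tVNS.
- **Run Friedman in each arm separately.** A significant result in the active arm alone can arise by chance and be read as benefit.
- **Treat the name as a slip and choose another test.** The choice of test and of time point then stays open until the data are seen.

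Aim 2 is one of the study's two aims, and Fugl-Meyer is the only clinical measure with a named test.

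**Working it through.** **1. The plan's own figure.** Section 12 enrols 36 "in order to achieve a target of at least fifteen subjects per treatment group" with 10-15% drop-out. Two arms of 15 make 30. At 15% drop-out, 30 / 0.85 = 35.3, rounded up to 36. At 10%, 30 / 0.90 = 33.3, rounded up to 34. The figure of 36 is reproduced, it assumes two separate groups, and nothing below changes it.

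**2. Structure of the test.** With n patients, k = 3 visits and R_j the sum over patients of the ranks at visit j, the statistic without ties is

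χ² = [12 / (n k (k + 1))] Σ R_j² − 3 n (k + 1).

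Each patient contributes the ranks 1, 2 and 3, which always total 6. A patient's overall level drops out, and arm appears nowhere in the formula. A correction for ties uses only the same within-patient ranks.

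**3. Numerical confirmation.** In one simulated data set of 30 patients and three visits, the statistic was 19.4. Over 1,000 random reallocations of the arm labels it took that single value. Adding 20 points to every score in one arm also left it at 19.4. This result needs no assumption about gains or SDs.

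**4. Size of the problem if the test is run literally (illustration).** The 15 per arm comes from Section 12. The documents give no expected sham gain, SD of change, correlation or alpha, so the following are assumptions: admission scores uniform on 12 to 44 (the eligibility range in Section 7), scores rounded and kept within 0 to 66, normal change with SD 4, 5, 6 or 8, correlation 0.7 between the discharge and 3-month changes, and two-sided 0.05. The 3-point gain is borrowed from the Section 10 threshold. There were 10,000 trials per scenario, with no tVNS effect.

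| Equal gain in both arms | Pooled Friedman significant, SD 4/5/6/8 | Significant in active arm only, SD 4/5/6/8 |
|---|---|---|
| 3 points, kept at 3 months | 95/80/64/41% | 21/25/24/17% |
| 3 points, halved by 3 months | 92/75/57/36% | 24/24/21/15% |
| 2 points, kept | 67/46/34/20% | 23/18/15/11% |
| 1 point, kept | 22/15/12/9% | 11/9/7/6% |
| none | 5/5/5/5% | 5/4/5/4% |

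Over all the no-effect scenarios, between-arm tests rejected at close to the nominal rate: rank-sum on change 4.2-5.3%, ANCOVA at discharge 4.6-5.7%, ANCOVA at 3 months 4.6-5.4%, van Elteren 4.4-5.4%.

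**5. Check on the last column.** If both arms have the same probability p of a significant Friedman result, the active arm alone is significant with probability p(1 − p), which cannot exceed 0.25. For a 3-point gain and SD 4, the active arm is significant in 0.210 + 0.471 (both arms) = 0.681 of trials, and 0.681 × 0.319 = 0.217, against 0.210 simulated. For SD 5, 0.253 + 0.239 = 0.492, and 0.492 × 0.508 = 0.250, against 0.253.

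**6. Sensitivity.** With a kept 3-point gain and correlation 0.5, pooled Friedman rejects in 96/82/66/41%. With 18 per arm it rejects in 98/88/74/48%. A different data model (between-patient SD 9, visit-to-visit SD 3, 15 per arm, 4,000 trials) gives 94% for pooled Friedman and 5.0% for a rank-sum test on change.

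**The case against.** The strongest reply is that nobody would run a pooled Friedman test under this sentence. It specifies two factors, one of them condition, and a pooled Friedman test has no condition factor. Arm-by-arm testing is not mentioned either. The natural reading is a mislabelled rank-based analysis of condition by time, so what is shown is a wrong test name and not a plan to claim benefit from change over time. This has force. A between-arm comparison is plainly intended, and the simulated rates should not decide how serious the point is. But the plan still names no procedure that makes the comparison, and the candidates differ in what they estimate and at which visit.

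It is also fair that the simulation inputs are not in the documents and that the pooled rate runs from about 5% to 95% across them. The same settings show pooled Friedman rejecting in only 36/26/19/13% of trials when tVNS truly adds 3 points and sham gains nothing. That contrast depends on setting the sham gain to zero: with sham gaining 3 and active 6, the rates are about 100/98/93/73%. No weight is placed on it.

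Section 4 describes both aims as within-subject comparisons in about 18 patients, which might seem to justify a within-patient test. It does not, because Section 11 gives each patient one condition. Even in a crossover, Friedman over six cells would be an omnibus test that does not separate condition from time.

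Finally, this is a secondary outcome in a pilot without a power calculation, and the primary EMG analysis is not affected. That limits the consequence but does not make the test fit the question.

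**Conclusion.** The concern holds. The only test named for Fugl-Meyer cannot use the condition factor listed with it, so the stated analysis cannot answer Aim 2. That conclusion follows from the form of the statistic and the parallel-group design and rests on no assumed figure.

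The practical size is conditional on the sentence being run as a Friedman test and on the assumed gains and SDs. With a shared gain of 3 points, a pooled test would be significant in 41% to 95% of trials in which tVNS does nothing, and arm-by-arm testing would favour the active arm alone in 17% to 25%. The pooled excess shrinks with the shared gain and disappears when neither arm improves. The point should be fixed. Enrolment of 36 and the EMG analysis are unaffected.

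**What to change.** Replace the Friedman sentence in Section 12 with one pre-specified between-arm analysis, and state whether discharge or 3 months carries the Aim 2 conclusion. Suitable choices are:

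- ANCOVA of Fugl-Meyer at the chosen visit, adjusted for admission score and randomisation stratum (below 23 against 23 to 44).
- A van Elteren test on change from admission, stratified the same way, if a rank method is preferred for an ordinal score.
- A mixed model with a condition-by-time term, or a rank-based factorial method for longitudinal data if the two-by-three layout is to be kept.

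These estimate different things, so one must be chosen. At 15 per arm the correct test will not be powerful. Under the assumptions above, with a true 3-point tVNS effect and no sham gain, ANCOVA at discharge rejects in 47/33/25/15% of trials for SD 4/5/6/8. The estimated difference and its confidence interval should therefore be reported with the p-value.

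The cost is one sentence, with no new patients, visits or data. It should be settled before the treatment codes are opened. The documents do not show whether that has happened; if it has, the replacement should be reported as chosen afterwards. As a separate wording point, the within-subject description and the figure of about 18 patients in Section 4 should be reconciled with the randomised design of 36.
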